8 ASSESSMENT OF SAFETY

8.1 SPECIFICATION OF SAFETY PARAMETERS

8.1.1 DEFINITION OF ADVERSE EVENTS (AE)

An adverse event (AE) is any noxious, unintended, or untoward medical occurrence that may appear or worsen in a subject during the course of a study. It may be a new intercurrent illness, a worsening concomitant illness, an injury, or any concomitant impairment of the subject's health, including laboratory test values, regardless of etiology. Any worsening (i.e., any clinically significant adverse change in the frequency or intensity of a pre-existing condition) should be considered an AE. A

diagnosis or syndrome should be recorded rather than the individual signs or symptoms of the diagnosis or syndrome.

Abuse, withdrawal, sensitivity or toxicity to an investigational product should be reported as an AE. An overdose, accidental or intentional, whether or not it is associated with an AE, should be reported. Any sequela of an accidental or intentional overdose of an investigational product should be reported as an AE. If the sequela of an overdose is an SAE, then the sequela must be reported on an SAE report form and as an AE.

The investigator or qualified designee will assess each subject to evaluate for potential new or worsening AEs as specified in the Schedule of Events and more frequently if clinically indicated. Adverse experiences will be graded and recorded throughout the study and during the follow-up period. The descriptions and grading scales found in the revised NCI Common Terminology Criteria for Adverse Events (CTCAE) version 5.0 will be utilized for adverse event reporting. (<http://ctep.cancer.gov/reporting/ctc.html>)

Toxicities will be characterized in terms regarding seriousness, causality, severity, duration, action taken, and outcome with regard to trial treatment.

Abnormal Laboratory Values

An abnormal laboratory value is considered to be an AE if the abnormality:

- Results in discontinuation from the study;
- Requires treatment, modification/ interruption of IP dose, or any other therapeutic intervention; or
- Is judged to be of significant clinical importance, e.g., one that indicates a new disease process and/or organ toxicity, or is an exacerbation or worsening of an existing condition.

Regardless of severity of grade, only laboratory abnormalities that fulfill a seriousness criterion need to be documented as a serious adverse event.

If a laboratory abnormality is one component of a diagnosis or syndrome, then only the diagnosis or syndrome should be recorded on the AE page/screen of the CRF. If the abnormality was not a part of a diagnosis or syndrome, then the laboratory abnormality should be recorded as the AE. If possible, the laboratory abnormality should be recorded as a medical term and not simply as an abnormal laboratory result (e.g. record thrombocytopenia rather than decreased platelets).

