The trial will be conducted in accordance with the ICH E6, the Code of Federal Regulations on the Protection of Human Patients (45 CFR Part 46). The Principal Investigator will assure that no deviation from, or changes to the protocol will take place without prior agreement from the sponsor and documented approval from the Institutional Review Board, except where necessary to eliminate an immediate hazard(s) to the trial participants. All personnel involved in the conduct of this study have completed Human Subjects Protection Training.

I agree to ensure that all staff members involved in the conduct of this study are informed of their obligation to meet the above commitments.

Principal Investigator: [name]
Print/Type Name

Signed: _____ Date: _____

STUDY SUMMARY

- Title:** A Phase 2 Study of Fedratinib in Myelodysplastic /Myeloproliferative Neoplasms (MDS/MPNs) and Chronic Neutrophilic Leukemia (CNL)
- Objectives:**
- Primary Objective:
- 1.) To evaluate the efficacy of fedratinib in patients with MDS/MPNs and CNL
- Important Secondary Objectives:
- 1.) To evaluate the safety and tolerability of fedratinib in MDS/MPNs and CNL.
 - 2.) To evaluate the effect of fedratinib in MDS/MPNs and CNL on patient-reported outcomes.
- Endpoint**
- Primary Efficacy Endpoint
- 1.) Proportion of patients achieving a clinical response from baseline to week 24 as defined as complete remission (CR), partial remission (PR), or clinical benefit (CB) per Modified MDS/MPN IWG Proposed Response Criteria¹
- Safety and Tolerability Endpoints
- 1.) Frequency, duration, and severity of adverse events (AE) will be determined by performing physical exams, and evaluating changes in vital signs, serum chemistry, hematology and urinalysis results using CTCAE version 5.0.
 - 2.) Proportion of patients experiencing grade ≥ 3 AE as defined by CTCAE v.5.0
- Important Secondary Efficacy Endpoints:
- a. Proportion of patients achieving spleen response at week 12 in patients with baseline splenomegaly.
 - b. Proportion of patients achieving spleen response at week 24 in patients with baseline splenomegaly.
 - c. Proportion of patients who have a 50% reduction in MPN-SAF TSS from baseline to week 12 in patients with baseline TSS ≥ 10
 - d. Proportion of patients who have a 50% reduction in MPN-SAF TSS from baseline to week 24 in patients with baseline TSS ≥ 10
 - e. Change in TSS from baseline to week 12 in patients with baseline TSS ≥ 10

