4.2.2 SECONDARY ENDPOINTS

- To evaluate the safety and tolerability of fedratinib in MDS/MPNs and CNL we will:
 - Measure the frequency, duration, and severity of AEs per CTCAE v.5.0 using information from physical exams, evaluation of changes in vital signs, serum chemistry, and hematology.
 - Determine the proportion of patients experiencing grade ≥ 3 AE as defined by CTCAE v.5.0
- To evaluate the efficacy of fedratinib on splenomegaly in MDS/MPNs and CNL we will:
 - Determine the proportion of patients who have a spleen response at week 12 as per Modified MDS/MPN IWG Proposed Response Criteria or demonstration of $\geq 35\%$ spleen volume reduction.
 - Determine the proportion of patients who have a spleen response at week 24 as per Modified MDS/MPN IWG Proposed Response Criteria or demonstration of $\geq 35\%$ spleen volume reduction.
- To evaluate the efficacy of fedratinib on patient-reported outcomes in MDS/MPNs and CNL we will:
 - Determine the proportion of patients who have a 50% reduction in MPN-SAF TSS from baseline to week 12 in patients with baseline TSS ≥ 10
 - Determine the proportion of patients who have a 50% reduction in MPN-SAF TSS from baseline to week 24 in patients with baseline TSS ≥ 10
 - Measure the change in TSS from baseline to week 12 in patients with baseline TSS ≥ 10
 - Measure the change in TSS from baseline to week 24 in patients with baseline TSS ≥ 10
 - Measure the change in TSS from baseline to time of best response in patients with baseline TSS ≥ 10
 - Measure patients' global impression of change (PGIC) at week 12
 - Measure PGIC at week 24

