Thrombocytopenia	Grade 4 or Grade 3 with bleeding	
 • Hold until resolved to $> 50 \times 10^9/L$ or baseline, if baseline was lower than $50 \times 10^9/L$. • Restart dose at 100 mg daily below last given dose. • If grade 4 thrombocytopenia persists for > 14 days, then discontinue study drug.
Neutropenia	Grade 4	
 • Interrupt dose until ANC $> 1.0 \times 10^9/L$. Restart dose at 100 mg daily below the last given

		
dose.
 
 If grade 4 neutropenia persists for > 14 days, discontinue study drug.
--	--	--

Other Toxicities	
Any Grade 1 or Grade 2	Continue study drug treatment and treat the toxicity; monitor as clinically indicated
Any grade 3 toxicity, if clinically significant and not manageable by supportive care	
 Interrupt study drug up to 2 weeks (14 days); until toxicity resolves to ≤ Grade 1 or baseline. Resume study drug at same dose. If assessed as at least possibly related to study drug, resume at next lower dose; monitor as clinically indicated
Any recurrent Grade 3 toxicity at 100 mg daily dose (lowest dose allowed on study) that is at least possibly related to study drug	
 Discontinue study drug and follow-up per Protocol. Exceptions require approval of study PI.
Any other non-hematologic Grade 4 toxicity	
 Discontinue study drug and follow-up per protocol
New red blood cell (RBC) transfusion requirement	
 Dose reduction should be considered in patients who become newly dependent upon RBC transfusions.

Dose reductions will be made in increments of 100 mg with 100 mg daily being the lowest dose to be administered on study. Any toxicity that occurs at a dose level of 100 mg daily that would require a dose reduction will result in discontinuation of study drug unless otherwise approved by the study PI.

Dose increases can occur after a dose reduction if toxicity has remained ≤ 1 or at baseline for ≥ 28 days. Dose increases will be made in increments of 100 mg daily may only occur once per cycle. Dose levels can only be tried on three occasions.

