10.4.4 SAFETY ANALYSES

Using summary statistics, safety data will be coded using CTCAE 5.0 criteria, with each AE being counted only once for a given participant. The severity, frequency, duration, outcome and relationship of AEs to the study agent, as defined by the treating investigator, will be presented by System Organ Class (SOC) and preferred term groupings. Adverse events leading to premature discontinuation from the study drug, adverse events of special interest, and serious treatment-emergent AEs will be presented in a table.

The proportion of patients experiencing grade ≥ 3 AEs will be calculated and presented separately in a table. Hematologic grade ≥ 3 AEs will be included if not present at baseline.

Hematologic values (hemoglobin, WBC, platelet count) will be calculated at the beginning of each cycle with median values being presented as a function of time while receiving treatment with study drug.

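### The grade ≥3 AE proportion is meant to reflect CTCAE-graded hematology, but whether an unacted-on grade 3 neutropenia or non-bleeding grade 3 thrombocytopenia counts depends on each investigator's judgement

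*Combined protocol and SAP*

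**What the plan says.** **Endpoint.** The Study Summary bases AE frequency, duration and severity on examinations and on "evaluating changes in vital signs, serum chemistry, hematology and urinalysis results using CTCAE version 5.0". Section 4.2.2 repeats this, "using information from physical exams, evaluation of changes in vital signs, serum chemistry, and hematology", and names the proportion of patients with a grade ≥3 AE as a separate safety measure.

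**Analysis.** Section 10.4.4 states: "The proportion of patients experiencing grade ≥ 3 AEs will be calculated and presented separately in a table". It adds one hematologic condition: "Hematologic grade ≥ 3 AEs will be included if not present at baseline". The only other hematology output is the median hemoglobin, white cell count and platelet count at the start of each cycle.

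**What makes a laboratory value an AE.** Section 8.1.1 says "An abnormal laboratory value is considered to be an AE if the abnormality" meets one of three conditions. The first is that it leads to discontinuation. The second is "Requires treatment, modification/ interruption of IP dose, or any other therapeutic intervention; or". The third is a judgement that it is clinically important, with organ toxicity and worsening of an existing condition among the examples. Section 8.4.1 also leaves the clinical significance of each abnormal result to the investigator.

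**What forces action.** In the hematology part of the 6.1.6 table, the thrombocytopenia trigger is "Grade 4 or Grade 3 with bleeding" and the neutropenia trigger is grade 4.

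**The concern.** The endpoint text points to graded laboratory changes, while the rule that admits a laboratory value to the AE dataset does not use grade. Where the protocol requires an action, the second condition in 8.1.1 admits the event. Where it requires none and nobody intervenes, only the third condition is left, and that is individual judgement at four sites.

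Section 2.3.1 names anemia and thrombocytopenia as the drug's most common hematologic events, so part of this gap lies where events are expected. With 25 patients and no control arm, uneven recording cannot be seen by comparison with another group. The reported toxicity rate would then depend partly on how each site applies 8.1.1.

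**Working it through.** The documents state no expected grade ≥3 rate, so there is no figure to reproduce. The check follows each type of laboratory event through the rules, then sizes one missed patient.

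**1. Which grade 3 events reach the AE dataset without relying on judgement?**

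| Grade 3 event | Required response in the protocol | Enters through 8.1.1 |
|---|---|---|
| ALT/AST, amylase/lipase, creatinine | Interruption at grade 3 or 4 (6.1.6) | Yes, second condition |
| Anemia treated with transfusion or an ESA (7.7), or leading to a dose reduction (6.1.6) | Intervention given | Yes, second condition |
| Thrombocytopenia with bleeding | Hold (6.1.6) | Yes, second condition |
| Thrombocytopenia without bleeding, not acted on | None in the hematology rows | Only if judged important |
| Neutropenia, not acted on | None in the hematology rows | Only if judged important |

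The general grade 3 row in 6.1.6 does not close the last two lines. It applies only when the toxicity is clinically significant and supportive care cannot manage it, which again is a judgement.

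**2. Would another planned output reveal the omission?** No. A median by cycle does not show how many patients reached grade 3, it uses start-of-cycle values only, and neutrophils are not among the three counts listed. Section 10.4.4 plans no worst-grade or shift table.

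**3. Are the data available?** Yes. The Schedule of Events (7.3.7) has a CBC with differential at every visit, and section 14.1 has clinical laboratory data entered in the study database.

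**4. Size per patient.** The safety set is all treated patients (10.3), planned as 25. A patient whose only grade ≥3 event goes unrecorded changes the proportion by 1/25 = 0.04, or 4 points.

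Illustration with assumed true counts:

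| True count | True proportion | 1 missed | 3 missed | 5 missed |
|---|---|---|---|---|
| 15/25 | 60% | 14/25 = 56% | 12/25 = 48% | 10/25 = 40% |
| 10/25 | 40% | 9/25 = 36% | 7/25 = 28% | 5/25 = 20% |

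The exact 95% interval is 38.7% to 78.9% for 15/25 and 21.1% to 61.3% for 10/25.

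**5. Worst-case range on assumed rates.** Let q be the share of patients with an unacted-on grade 3 value and p the share with another counted grade ≥3 AE. Take the two as independent and suppose no such value is ever recorded by judgement. The understatement is (1 − p) × q.

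- p = 0.6, q = 0.1: 0.4 × 0.1 = 0.04
- p = 0.4, q = 0.3: 0.6 × 0.3 = 0.18

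That is 4 to 18 points. If half of these values were recorded by judgement, it would be 2 to 9 points. Neither p nor q comes from the documents.

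**The case against.** The strongest reply is that the protocol already captures these events. Section 8.1.1 says if, not only if. Its general definition names laboratory values as possible AEs, and its third condition cites organ toxicity and worsening of an existing condition, which a new grade 3 cytopenia fits readily. Section 8.4.1 requires every abnormal result to be appraised. Section 10.4.4 has its own sentence on hematologic grade ≥3 events. Section 6.1.6 also refers to the US Package Insert, which is not in the documents and may add actions.

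Much of this stands. Many investigators would record such an event, so a reader who infers that 8.1.1 excludes grade 3 cytopenias, or that the proportion is necessarily biased downward, goes further than the text. So does a reader who takes 4.2.2 to make every graded value an AE, since it names sources of information and sets no counting rule. Extending the point to chemistry is not supported either, because grade 3 or 4 elevations of the listed tests require interruption.

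What remains is narrower. Unless the three conditions in 8.1.1 limit something, the list has no function. The hematologic sentence in 10.4.4 speaks of AEs, so it applies after 8.1.1 and not in place of it. Recording by many investigators is not uniform recording.

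**Conclusion.** The point holds for new grade 3 neutropenia, and for new grade 3 thrombocytopenia without bleeding, that nobody acts on. The plan does not settle whether these count toward the grade ≥3 proportion, the answer can differ by site, and no planned table would show the difference.

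The size cannot be derived from the documents. The assumption-free statement is 4 points per affected patient at n = 25. A reader might take the 4 to 18 point range as an estimate of bias. It is not one: its inputs are assumed, it supposes that judgement never captures an event, and it would shrink if grade 3 events cluster in the same patients.

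This is a descriptive secondary safety endpoint. The primary response analysis, the interim rule and the sample size are untouched. It merits a short clarification because it can be settled from data already collected.

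**What to change.** In section 10.4.4:

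1. Derive each patient's worst post-baseline CTCAE v5.0 grade for hemoglobin, neutrophils and platelets from the recorded values, whether or not any action was taken.
2. Count a derived grade ≥3 only if it was not present at baseline, in line with the existing sentence in 10.4.4. This condition is essential. Section 5.2 admits platelets down to 35 × 10⁹/L and sets no hemoglobin floor, so without it unchanged disease-related cytopenia would be counted as toxicity.
3. Report the proportion of patients with either a reported grade ≥3 AE or a new derived hematologic grade ≥3, beside the proportion based on reported AEs alone.
4. Add a shift table of baseline grade against worst post-baseline grade for the three parameters.

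The AE and SAE reporting rules in section 8 and the dose rules in 6.1.6 stay as they are. The cost is a short text change and one extra derivation from laboratory data already entered. The stated toxicity rate may be higher than under reported AEs alone, and the side-by-side presentation shows by how much.

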8.1.2 DEFINITION OF SERIOUS ADVERSE EVENTS (SAE)

A qualified Investigator will evaluate all adverse events as to their seriousness. A serious adverse event (SAE) is any AE occurring at any dose that:

- Results in death;
- Is life-threatening (i.e., in the opinion of the Investigator, the subject is at immediate risk of death from the AE);
- Requires inpatient hospitalization or prolongation of existing hospitalization (hospitalization is defined as an inpatient admission, regardless of length of stay);

- Results in persistent or significant disability/incapacity (a substantial disruption of the subject's ability to conduct normal life functions);
- Is a congenital anomaly/birth defect;
- Constitutes an important medical event

Important medical events are defined as those occurrences that may not be immediately life threatening or result in death, hospitalization, or disability, but may jeopardize the subject or require medical or surgical intervention to prevent one of the other outcomes listed above. Medical and scientific judgment should be exercised in deciding whether such an AE should be considered serious.

Events not considered SAEs are hospitalizations for:

- A standard procedure for protocol therapy administration. However, hospitalization or prolonged hospitalization for a complication of therapy administration will be reported as an SAE.
- Routine treatment or monitoring of the studied indication not associated with any deterioration in condition.
- The administration of blood or platelet transfusion as routine treatment of studied Indication. However, hospitalization or prolonged hospitalization for a complication of such transfusion remains a reportable SAE.
- A procedure for protocol/disease-related investigations (e.g., surgery, scans, endoscopy, sampling for laboratory tests, bone marrow sampling). However, hospitalization or prolonged hospitalization for a complication of such procedures remains a reportable SAE.
- Hospitalization or prolongation of hospitalization for technical, practical, or social reasons, in absence of an AE.
- A procedure that is planned (i.e., planned prior to starting of treatment on study); must be documented in the source document and the CRF. Hospitalization or prolonged hospitalization for a complication remains a reportable SAE.
- An elective treatment of or an elective procedure for a pre-existing condition unrelated to the studied indication.
- Emergency outpatient treatment or observation that does not result in admission, unless fulfilling other seriousness criteria above.

8.1.3 DEFINITION OF UNANTICIPATED PROBLEMS

Unanticipated problems (UPs) involving risks to participants or others to include, in general, any incident, experience, or outcome that meets all of the following criteria:

- Unexpected in terms of nature, severity, or frequency given (a) the research procedures that are described in the protocol-related documents, such as the IRB-approved research protocol and informed consent document; and (b) the characteristics of the participant population being studied;
- Related or possibly related to participation in the research ("possibly related" means there is a reasonable possibility that the incident, experience, or outcome may have been caused by the procedures involved in the research); and
- Suggests that the research places participants or others at a greater risk of harm

(including physical, psychological, economic, or social harm) than was previously known or recognized.

8.2 CLASSIFICATION OF AN ADVERSE EVENT

8.2.1 SEVERITY OF EVENT

For both AEs and SAEs, the Investigator must assess the severity / intensity of the event.

The severity/intensity of AEs will be graded based upon the subject's symptoms according to the current active minor version of the Common Terminology Criteria for Adverse Events (CTCAE, Version 5.0);

http://ctep.cancer.gov/protocolDevelopment/electronic_applications/ctc.htm#ctc_50

AEs that are not defined in the CTCAE should be evaluated for severity/intensity according to the following scale:

- Grade 1 = Mild – transient or mild discomfort; no limitation in activity; no medical intervention/therapy required
- Grade 2 = Moderate – mild to moderate limitation in activity, some assistance may be needed; no or minimal medical intervention/therapy required
- Grade 3 = Severe – marked limitation in activity, some assistance usually required; medical intervention/therapy required, hospitalization is possible
- Grade 4 = Life-threatening – extreme limitation in activity, significant assistance required; significant medical intervention/therapy required, hospitalization or hospice care probable
- Grade 5 = Death - the event results in death

The term “severe” is often used to describe the intensity of a specific event (as in mild, moderate or severe myocardial infarction); the event itself, however, may be of relatively minor medical significance (such as severe headache). This criterion is not the same as “serious” which is based on subject/event outcome or action criteria associated with events that pose a threat to a subject's life or functioning.

Seriousness, not severity, serves as a guide for defining regulatory obligations.

For both AEs and SAEs, the Investigator will provide a record of the start and stop dates of the event.

8.2.2 RELATIONSHIP TO STUDY AGENT

For all collected AEs, the investigator will evaluate the participant and will determine the AE's causality based on temporal relationship and his/her clinical judgment. Causality should be assessed and provided for every AE/SAE based on currently available information. Causality is to be reassessed and provided as additional information becomes available.

The degree of certainty about causality will be graded using the categories below.

- **Definitely Related** – There is clear evidence to suggest a causal relationship, and other possible contributing factors can be ruled out. The clinical event, including an abnormal

laboratory test result, occurs in a plausible time relationship to drug administration and cannot be explained by concurrent disease or other drugs or chemicals. The response to withdrawal of the drug (dechallenge) should be clinically plausible. The event must be pharmacologically or phenomenologically definitive, with use of a satisfactory rechallenge procedure if necessary.

- **Probably Related** – There is evidence to suggest a causal relationship, and the influence of other factors is unlikely. The clinical event, including an abnormal laboratory test result, occurs within a reasonable time after administration of the drug, is unlikely to be attributed to concurrent disease or other drugs or chemicals, and follows a clinically reasonable response on withdrawal (dechallenge). Rechallenge information is not required to fulfill this definition.
- **Possibly Related** – There is some evidence to suggest a causal relationship (e.g., the event occurred within a reasonable time after administration of the trial medication). However, other factors may have contributed to the event (e.g., the participant's clinical condition, other concomitant events). Although an AE may rate only as "possibly related" soon after discovery, it can be flagged as requiring more information and later be upgraded to "probably related" or "definitely related," as appropriate.
- **Unlikely to be related** – A clinical event, including an abnormal laboratory test result, whose temporal relationship to drug administration makes a causal relationship improbable (e.g., the event did not occur within a reasonable time after administration of the trial medication) and in which other drugs or chemicals or underlying disease provides plausible explanations (e.g., the participant's clinical condition, other concomitant treatments).
- **Unrelated** – The AE is completely independent of study drug administration, and/or evidence exists that the event is definitely related to another etiology. There must be an alternative, definitive etiology documented by the clinician.

